2 OVERVIEW OF STUDY DESIGN

This is a post-market, prospective, randomized, open label, multicenter, controlled study to evaluate the effectiveness of closed incision negative pressure therapy (ciNPT) compared to standard of care (SOC) surgical dressing in reducing the surgical site complications (SSCs) in subjects with revision of a failed total knee arthroplasty (TKA).

Each potential study participant will complete the procedures and assessments listed in Protocol Sections 4.1 and 4.2 by the Investigator or designee within 30 days prior to study start. Only subjects who meet all pre-operative and intra-operative eligibility criteria will be randomized in the study. Each enrolled subject will be randomized in a 1:1 ratio to receive either ciNPT or SOC after a revision TKA. The anticipated maximum participation for each subject from screening initiation to the last visit is up to 134 days.

2.1 Sample Size and Power

The primary endpoint of this study is the subject incidence of SSC. The incidence rates of SSC are different for septic and aseptic revisions; the assumed SSC rate is 33% for septic and 6.9% for aseptic. This study plans to enroll at least 50% septic revisions overall. These enrollment rates lead to an assumed pooled SSC rate of 20% in the SOC dressing arm.

Assuming an overall type 1 error rate of 0.05, with a two-sided hypothesis test, the study will have at least 80% power to detect a difference of 10% (50% reduction) in SSCs in the ciNPT arm with 199 subjects in each treatment arm, with one interim analysis at about 50% of the evaluable subjects for a total of 398

subjects using the likelihood ratio test. With an estimated 5%-10% loss, a non-binding interim analysis for superiority at approximately 50% of the evaluable subjects using O'Brien-Fleming method for monitoring boundaries, the planned sample size will be inflated for a potential loss of follow-up for a total of 440 subjects.

2.2 Study Population and Subpopulations

The study population will consist of subjects undergoing a revision of a failed total knee arthroplasty (TKA). Per Section 8.4.2 and Section 8.4.3 of the study protocol, the overall study population can be further partitioned into two predefined subpopulations (Septic versus Aseptic) based on the TKA revision type.

2.3 Treatments

ciNPT: Subjects randomized to ciNPT will receive treatment for a duration consistent with the Instructions for Use (IFU) document included with the selected Prevena™ Dressing but no shorter than five days post-surgery. Depending on the length of the incision, an appropriate Prevena™ Dressing will be used to cover the closed surgical incision, according to the instructions for use included with the product. Total treatment time should not exceed the maximum number of days indicated in the IFU document included with the Prevena™ Dressing applied immediately following surgery. For the delivery of negative pressure, an ActiV.A.C.® (The ActiV.A.C.® Unit is set to 125mmHg of continuous negative pressure) or Prevena Plus™ 125 Therapy Unit will be attached to the dressing tubing, and ciNPT will be initiated in the operating room.

Standard of Care (SOC): Subjects randomized to standard of care will have their closed surgical incision covered with the silver-impregnated dressing, Aquacel® Ag Surgical or other equivalent, up to the maximum number of days specified in the IFU but no shorter than five days post-surgery. Total treatment time should not exceed the maximum number of days indicated in the IFU document included with the dressing applied immediately following surgery.

2.4 Randomization

Subjects who meet all inclusion criteria and no exclusion criteria will be randomized in a 1:1 ratio to either the ciNPT or SOC dressing treatment arm. The randomization will be stratified by status at revision (septic versus aseptic).

For each stratum, a randomization schedule including randomization numbers and treatment assignments will be generated and maintained centrally in the web-based clinical database management system. Once randomized, a subject's assignment cannot be altered or changed; a subject should not be randomized twice.

2.5 Schedule of Events and Visits

A detailed schedule of events and visits for the study is provided in Table 1.

Table 1: Schedule of Events

V2.0 August 8, 2019

	Screening	TKA Revision		End of Treatment	Midterm Follow-up	Long Term Follow-up	Unscheduled
		Pre	Post				
	Day -30 to 0	Day0	Day0	Per Dressing IFU	Day 30-45	Day 90 (+14 days)	
Informed Consent	X						
Pre-Operative Inclusion & Exclusion Criteria	X						
Demographics & Subject Characteristics	X						
Vital Signs	X	X ²					
Medical & Surgical History	X	X ³					
Laboratory Assessment for Pregnancy ¹	X	X					
Intra-operative Inclusion & Exclusion Criteria			X				
TKA Revision Procedure			X				
Randomization			X				
Application of Study Treatment			X				
Removal of Study Treatment				X			
SSC Assessment				X	X	X	X
Intervention Assessment				X	X	X	X
Pain Assessment		X	X ⁴	X			
Patient-Reported Outcomes Assessments (KOOS and PROMIS Global-10)	X			X	X	X	
Healthcare Utilization Assessment				X	X	X	X
End of Study						X	X ⁵
Concomitant Medications	X	X	X	X	X	X	X
Adverse Event Assessment and SAE Reporting			X	X	X	X	X

1 - Assessed on women of child-bearing potential
2 - Weight only
3 - Updates to medical and surgical history to be documented.
4 - Pain will be assessed at the earlier of discharge or 24 hours (± 2 hours) after the TKA Revision.
5 - End of Study assessed at an unscheduled visit only when a subject discontinues prior to the 90-day visit.

3 STUDY OBJECTIVE

The objective of this study is to evaluate surgical site complications (SSC) in subjects undergoing a revision of a failed total knee arthroplasty (TKA) when closed incision negative pressure therapy (ciNPT) is used to manage the closed incision, as compared to standard of care (SOC) surgical dressing.

4 STUDY ENDPOINTS

4.1 Primary Endpoint

The primary endpoint is the subject incidence of Investigator-assessed surgical site complications (SSCs) within 90 days of TKA revision in subjects treated with ciNPT as compared to standard of care (SOC) surgical dressing. SSCs include any occurrence of superficial surgical site infection (SSI), deep SSI, dehiscence, seroma, hematoma, skin necrosis, or continued drainage as outlined in Section 4.11.1 of the study protocol. Three possible values for the primary endpoint are:

- “Occurred”: If the subject had one or more occurrences of SSC on or before 90 days post TKA revision;
- “No occurrences”: If the subject had an assessment of SSC on or after 90 days post TKA revision and had no known occurrence of any SSC within 90 days of the TKA revision.
- “Incomplete follow-up”: If the subject had no known occurrences of SSC and did not have any SSC assessment at least 90 days post TKA revision.

The start date of the complication will be recorded in order to calculate the number of days from the revision surgery until occurrence of the event.

4.2 Secondary Endpoints

4.2.1 Subject Incidence SSI

This secondary endpoint is the subject incidence of any Investigator-assessed SSI (superficial or deep) within 90 days of TKA revision in subjects treated with ciNPT as compared to SOC dressing. Superficial SSI and deep SSI are components of the primary endpoint. Subjects will be categorized using methods similar to those described in section 4.1 of this document.

4.2.2 Subject Incidence Deep SSI

This secondary endpoint is the subject incidence of any Investigator-assessed deep SSI within 90 days of TKA revision in subjects treated with ciNPT as compared to SOC dressing. Deep SSI is a component of the primary endpoint. Subjects will be categorized using methods similar to those described in section 4.1 of this document.

4.3 Exploratory Endpoints

Exploratory endpoints for this study include:

4.3.1 Pain Assessment

- Worst pain last 24 hours
- Average pain in last 24 hours

The pain assessment consists of two self-administered questions used to evaluate the severity of a subject's pain in the past 24 hours post TKA revision.

Subjects will respond using the integer value. All efforts will be made to ensure the subject completes both pain assessments at each scheduled visit: Day 0 pre-TKA revision, Day 0 post-TKA revision and End of Treatment.

4.3.2 Knee Injury and Osteoarthritis Outcome Subscale Score (KOOS)

The KOOS instrument is a patient-reported questionnaire to assess short-term and long-term symptoms and functions. KOOS consists of 5 subscales:

- KOOS: Knee-Related Quality of Life (QOL)
- KOOS: Sport and Recreation Function (Sport/Rec)
- KOOS: Activities of Daily Living (ADL)
- KOOS: Pain
- KOOS: Other Symptoms

The scoring details are in Section 8.7.2. All efforts will be made to ensure the subjects complete the entire assessment at each scheduled visit: Baseline (Screening or Day 0), End of Treatment, Midterm Follow-up, and Long-Term Follow-up.

4.3.3 Patient-Reported Outcomes Measurement Information System (PROMIS) Global-10

- Mental health – as assessed by PROMIS Global 10 t-score
- Physical health – as assessed by PROMIS Global 10 t-score

The PROMIS Global-10 is a generic health assessment that measures the physical, social, and emotional health of individuals and is often used for those living with chronic conditions. The scoring methods can be found in Section 8.7.3. All efforts will be made to ensure the subject completes the entire assessment, which consists of 10 questions, at each scheduled visit: Baseline (Screening or Day 0), End of Treatment, Midterm Follow-up, and Long-Term Follow-up.

4.3.4 30-Day Subject Incidence of SSC

This endpoint is the subject incidence of any Investigator-assessed SSC within 30 days post TKA revision in subjects treated with ciNPT as compared to SOC dressing. Subjects will be categorized using methods similar to those described in section 4.1 of this document.

4.3.5 45-Day Subject Incidence of SSC

This endpoint is the subject incidence of any Investigator-assessed SSC within 45 days post TKA revision in subjects treated with ciNPT as compared to SOC dressing. Subjects will be categorized using methods similar to those described in section 4.1 of this document.

4.4 Safety Endpoint

The safety endpoint is the subject incidence of adverse events (AEs). All captured AEs will be coded using the MedDRA coding dictionary version 20.1 or higher.

5 ANALYSIS SETS

The following analysis sets are planned for this study:

- Safety Analysis Set: The Safety Analysis Set consists of all randomized subjects who received any study-related treatment procedures. Subjects will be analyzed according to the study treatment they received immediately following the TKA revision.
- ITT Analysis Set: The ITT (intention-to-treat) Analysis Set consists of all randomized subjects. Subjects will be analyzed according to their randomized treatment assignment.
- mITT Analysis Set: The modified ITT Analysis Set will include subjects in the ITT analysis set with the following: 1) who had any SSC on or before 90 days post TKA revision, or 2) had an assessment of SSC on or after 90 days post TKA revision and had no known occurrence of any SSC within 90 days post the TKA revision. Subjects will be analyzed according to their randomized treatment assignment.
- Per-Protocol Analysis Set: This will include subjects in the mITT analysis set who had no disqualifying protocol deviation(s) that would impact the interpretation of the primary endpoint. The disqualifying protocol deviation(s) for exclusion from this set will be defined and documented in a treatment-blinded fashion prior to the final database lock by the Protocol Deviation Review Committee. Subjects will be analyzed according to their randomized treatment assignment.
- Modified Per-Protocol (mPP) Analysis Set: This will include subjects in the Per-Protocol analysis set excluding any subjects who received prohibited therapy as described in Section 4.15 of the study protocol or any subjects that received alternative therapy following the study treatment period.

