5.2.4. Weekly Visit (Study Treatment Visits)

The following procedures and assessments will be performed and documented.

- Removal of Study Treatment
- SSC Assessment
- Intervention Assessment
- Pain Assessment
- PRO assessments (KOOS and PROMIS Global-10)
- Healthcare Utilization Assessment
- Concomitant Medications
- AE Assessment and SAE Reporting

5.2.5. Midterm Follow-up/Day 30 to 45

The following procedures and assessments will be performed and documented.

- SSC Assessment
- Intervention Assessment
- PRO assessments (KOOS and PROMIS Global-10)
- Healthcare Utilization Assessment
- Concomitant Medications

- AE Assessment and SAE Reporting

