8.7 Exploratory Endpoint Analyses

In general, analyses listed below will be performed on subjects in the ITT analysis set unless otherwise specified. Analyses including revision type will be based on per actual revision type.

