Both Global Physical Health and Global Mental Health T-Scores and their corresponding changes from baseline will be summarized separately by treatment arm and by visit. Changes from baseline for both Global Physical Health and Global Mental Health T-Scores will be analyzed separately using a mixed model, which includes (“Treatment Arm” and “Visit”) plus the interaction term (“Treatment Arm by Visit”), revision type, clinical site, and with subject as a random effect. LS means along with 95% confidence intervals and p-values at each post-baseline timepoint will be presented.

If a missing data rate for Global Physical Health or Global Mental Health is 10% or greater, then an approach of multiple imputation based on Rubin’s [1976, 1987]^{3,4} for missing data for both Global Physical Health and Global Mental Health will be used by creating several different plausible imputed data sets and appropriately combining results obtained from each of them. A basic description of the multiple imputation includes:

1. Using SAS procedures including Proc MI and Proc MIANALYZE;
2. Using the fully conditional specification (FCS) method / algorithm [Brand 1999 and van Buuren 2007]^{5,6} which is a linear regression for continuous variables;
3. Including treatment arm, age (≥ 65 or < 65 years), sex, BMI (≥ 35 kg/m² or < 35 kg/m²), race/ethnicity, material used in the TKA revision, and co-morbidities in the imputation model;
4. Creating five imputed datasets [Rubin 1996]⁷;
5. Combining completed-data estimates from five imputed datasets.

The mixed model analysis for both Global Physical Health and Global Mental Health described above will be repeated based on the imputed data.

8.7.4 30-Day Subject Incidence of SSC Analysis

The proportion of subjects with each value of “Occurred” or “No occurrences” or “Incomplete-Follow-up” for 30-Day SSC will be summarized, as applicable, by treatment arm based on the ITT, mITT analysis sets. Additionally, 30-Day SSC events by type: superficial SSI, deep SSI, dehiscence, seroma, hematoma, skin necrosis, or continued drainage will be summarized based on the mITT analysis set.

Superiority Testing

The following hypothesis will be tested for superiority:

Null H_0 : $\Delta_{\text{ciNPT-SOC}} = 0$

Alternative H_a : $\Delta_{\text{ciNPT-SOC}} \neq 0$

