where $\Delta_{\text{ciNPT-SOC}}$ is the difference in the proportion of subjects in the ciNPT arm with at least one SSC and the proportion of subjects in the SOC dressing arm with at least one SSC.

For the combined population, a Cochran-Mantel-Haenszel (CMH) test stratified by type of revision (Septic, Aseptic) will be used to compare the SSC incidence rates between two treatment arms based on the mITT analysis set. The odds ratio and its asymptotic 95% confidence interval will be computed. This test is equivalent to the test of difference for the proportions.

For the septic and aseptic subpopulations, a Chi-square or Fisher's test, as appropriate will be performed within each revision type for SSC incidence rates between treatment arms based on the corresponding mITT analysis set.

Additionally, figure(s) may be generated to display the results from the analyses of this endpoint graphically.

8.7.5 45-Day Subject Incidence of SSC Analysis

Any 45-Day subject incidence of SSC will be analyzed in a similar fashion as the 30-Day subject incidence of SSC endpoint described in section 8.7.4 of this document.

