8.7.6 Time to SSC Analysis

Time to SSC: defined as the time in day(s) from the date of TKA revision to the first SSC event and is calculated as:

$TTSSC = (\text{Start Date of the first SSC} - \text{Date of the TKA revision}) + 1$

Censoring will occur for the following:

- 1.) Subjects who experience their first SSC on the day of TKA revision after initial dressing application will be considered to have a time to SSC of 1 day.
- 2.) Subjects, who do not have any SSC assessment after initial dressing application and they withdraw before the first scheduled SSC assessment at the end of treatment, will be censored at the date of TKA revision.
- 3.) Subjects who do not have any SSC assessment at Day 90 will be censored at Day 90 or end of study date, whichever comes first.

A Kaplan-Meier curve will be generated for each treatment arm and the quartile estimates will be generated as well. A log-rank test will be used to compare the time-to-SSC between treatment arms. These analyses may be repeated utilizing data calculated from the additional way of calculation described above.

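### The 30-day SSC test uses an analysis set defined by 90-day status, so known 30-day non-events are dropped while every 30-day event is kept

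*SAP*

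**What the plan says.** SAP 5 defines a single mITT set. It holds subjects with any SSC by day 90, and subjects who "had an assessment of SSC on or after 90 days post TKA revision and had no known occurrence of any SSC" through that day. No 30-day or 45-day version is defined.

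SAP 4.3.4 defines the exploratory 30-day endpoint: "This endpoint is the subject incidence of any Investigator-assessed SSC within 30 days post TKA revision". It classifies subjects by the method of SAP 4.1, that is, as occurred, no occurrences or incomplete follow-up.

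SAP 8.7.4 uses two sets. The three-category table "for 30-Day SSC will be summarized, as applicable, by treatment arm based on the ITT, mITT analysis sets". The by-type summary, the stratified CMH test with its odds ratio, and the within-stratum tests use mITT; the CMH test "will be used to compare the SSC incidence rates between two treatment arms based on the mITT analysis set". SAP 8.7.5 repeats this for 45 days.

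The default in SAP 8.7 is ITT: "In general, analyses listed below will be performed on subjects in the ITT analysis set unless otherwise specified". Protocol 8.3.6 generally places exploratory analyses on ITT and/or mPP. SAP 10 does not list a move to mITT.

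The visit that settles 30-day status is Protocol 5.2.5, "Midterm Follow-up/Day 30 to 45". The next scheduled one is day 90 to 104.

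For time to SSC, SAP 8.7.6 says that subjects with no Day 90 assessment "will be censored at Day 90 or end of study date, whichever comes first". It adds: "These analyses may be repeated utilizing data calculated from the additional way of calculation described above". Only one calculation is described above that sentence. Protocol 8.1.1 counts days, for each SSC component, to the last assessment that found the subject free of the complication.

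**The concern.** Whether a subject enters the 30-day test depends on the 30-day outcome. Take two subjects who both leave the study on day 60. One had an SSC on day 20 and is in mITT. The other was examined on day 35 with no SSC. That subject counts as no occurrences at 30 days under SAP 4.3.4, but is not in mITT. The selection can remove only non-events, so each arm's 30-day rate is too high.

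If loss after Midterm differs between arms, which is possible in an open-label trial, the odds ratio moves as well. SAP 8.7.4 labels this comparison superiority testing, and SAP 1 allows planned analyses to go into submissions and manuscripts. The tested denominators will not match the ITT table in the same section.

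**Working it through.** **Inputs from the documents.** SOC 90-day SSC rate 20%, difference 10 points, 199 evaluable per arm, 5%-10% loss, 440 randomized 1:1 (SAP 2.1, Protocol 8.4.2).

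**The plan's own figures reproduce.**
- Pooled SOC rate: 0.5 × 33% + 0.5 × 6.9% = 19.95%.
- Two-proportion formula for 20% versus 10%, two-sided 0.05, 80% power: 199 per arm, 398 in total.
- 398 / (1 − 0.095) = 440, so the planned loss is 42 of 440 (9.5%).

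**Assumptions, because the documents give no figure.** Day-30 rates p of 15% (SOC) and 7.5% (ciNPT). Let d be the share of day-30 SSC-free subjects excluded from mITT for want of a day-90 assessment. If half of the planned loss falls after Midterm, d is 2.5%-5%. If all of it does, d is 5%-10%, which is the ceiling.

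**30-day rate in mITT** = p / (1 − d(1 − p)). **Known non-events dropped** = 220 × d × (0.85 + 0.925).

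| d | SOC (15%) | ciNPT (7.5%) | Relative inflation | Dropped of 440 |
|---|---|---|---|---|
| 2.5% | 0.15/0.97875 = 15.3% | 0.075/0.976875 = 7.7% | 2.2%, 2.4% | 10 |
| 5% | 0.15/0.9575 = 15.7% | 0.075/0.95375 = 7.9% | 4.4%, 4.8% | 20 |
| 10% | 0.15/0.915 = 16.4% | 0.075/0.9075 = 8.3% | 9.3%, 10.2% | 39 |

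**Odds ratio.** Dropping a share d of non-events divides an arm's odds by (1 − d). The mITT odds ratio is therefore 0.4595 × (1 − d_SOC)/(1 − d_ciNPT), where 0.4595 = (0.075/0.925)/(0.15/0.85).
- Equal loss: 0.459, unchanged.
- SOC 5%, ciNPT 2.5%: 0.448. Reversed: 0.472.
- SOC 10%, ciNPT 5%: 0.435. Reversed: 0.485.

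**Under no treatment effect.** This was simulated with 14% at day 30 in both arms, 220 per arm, an unstratified test at 0.05 and all loss after an SSC-free visit at or after day 30 (an upper bound). Equal loss of 9.5% rejects 5.0% of the time. Loss of 10% versus 5% rejects 5.7%, with a spurious difference of 0.8 point.

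**45 days.** A Midterm visit on days 30-44 does not settle 45-day status. Only subjects seen on day 45 or later and then missing day 90 are wrongly dropped, so the effect is smaller.

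**Time to SSC.** Assume a 20% SOC 90-day risk, 75% of SSCs by day 30, events spread evenly within each period, and close-out at or after day 90. The Kaplan-Meier shortfall under the SAP rule is 0.20 × (share lost) × (1 − F), where F is the fraction of SSCs that occur by the last assessment.
- Last seen day 38 (F = 0.783): 0.2-0.4 point for 5%-10% loss.
- Last seen day 10 (F = 0.25): 0.75-1.5 points.
- Close-out midway between the last visit and day 90: 0.1-0.3 and 0.5-1.1 points.
- End-of-study date is itself an SSC assessment: nil.

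For the log-rank test on the same assumptions (20% versus 10%, scaled to 220 per arm), the SAP rule and last-assessment censoring differ by less than 0.02 in z with equal loss. With 10% versus 5% loss they differ by about 0.05 (last seen day 38) and by 0.16-0.18 (every lost subject last seen day 10).

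**The case against.** The strongest reply is about weight, and most of it stands. The endpoints are exploratory, and Protocol 8.3.6 plans no multiplicity adjustment for them. The planned effect measure is the odds ratio, which equal loss leaves alone. On the assumed inputs the standard error of the log odds ratio is √(1/33 + 1/187 + 1/16.5 + 1/203.5) = 0.318 (95% CI about 0.25-0.86). The shifts to 0.448 and 0.435 are therefore only 0.08 and 0.17 standard errors.

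The exclusions will also be visible. SAP 8.1 reports subjects excluded from mITT with reasons, and SAP 8.7.4 tabulates ITT as well. A reader could rebuild unstratified 30-day proportions from that table, but not the stratified test or odds ratio. Disclosure does not make the 90-day set right for a 30-day question.

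On SAP 8.7.6, a reader might infer that the censoring rule is simply wrong, or that it overturns a planned protocol test. The documents support neither. Protocol 8.1.1 gives a per-component day count and plans no time-to-first-SSC test. Early end-of-study is recorded at an unscheduled visit (Protocol 5.1), which includes an SSC assessment (5.2.7), and Protocol 4.4.2 asks for SSC assessment before withdrawal. Last-assessment censoring has its own bias. If half of the otherwise missed SSCs are still reported, it overstates risk by 0.1-0.8 point, while the SAP rule understates it by 0.1-0.7.

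A reader might also extend the point to the SSI endpoints in SAP 8.6.1 and 8.6.2. Those run to day 90, so this mechanism does not operate there. mITT can hold a subject with another SSC whose 90-day SSI status is unknown, but Protocol 8.3.4 and 8.3.5 already imply excluding such subjects from the comparison.

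**Conclusion.** The 30-day point holds on the text. SAP 8.7.4 applies a 90-day set to a 30-day endpoint and removes known non-events only. The arm rates are biased upward by about 2%-5% in relative terms, or 4%-10% at the ceiling. The odds ratio is unchanged with equal loss and shifts slightly with unequal loss. SAP 8.7.5 shares the flaw with less effect.

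The sizes rest on assumed day-30 rates and an assumed timing of loss; only the 5%-10% loss is documented. A reader might infer a bias in favour of ciNPT. The documents do not support that, because the direction depends on which arm loses more subjects after Midterm, and nothing predicts this. The primary test and sample size are unaffected.

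The SAP 8.7.6 point is minor: a choice between imperfect conventions, and a reference to an alternative calculation that is never defined.

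**What to change.** In SAP 8.7.4 and 8.7.5, replace mITT with an evaluable set for each horizon t (30 or 45 days): subjects with an SSC by day t, plus subjects with an SSC assessment on or after day t and no known SSC through day t. A subject whose first SSC comes after day t stays in as a non-event at t. Record the analysis set in SAP 10, since Protocol 8.3.6 names ITT and/or mPP.

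In SAP 8.7.6, keep the current rule if preferred. Name censoring at the last SSC assessment, capped at 90 days after revision (91 on the SAP's scale, which adds one day), as the additional calculation. Label it a sensitivity analysis and do not claim that it is uniformly better.

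The cost is SAP wording before database lock, with no new data. Denominators will differ slightly between the 30-day, 45-day and 90-day tables, which a footnote can explain.
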